Change from Baseline to Weeks 104 and 208 in CSF biomarkers (i.e., CSF Weeks 104 and 208 only), including CXCL13, BAFF (B cell activating factor), TNF, IL-6, IL-10, IL-17, interferon-gamma, IL-4, IL-23, IL-8, soluble CD27 (sCD27), genetic risk factors (HLA-DRB1*15:01) or other emerging exploratory markers of disease biology as appropriate

Change from Baseline to Weeks 48, 104, and 208 in slowly evolving lesions (SEL)

Change from Baseline to Weeks 24, 48, 72, 104, 130, 156, 182 and 208 in peripheral blood immune cell population frequency and phenotype, including B cells, T cells and innate immune cells (monocyte, macrophage, neutrophils, natural killer cells, etc.)

Change from Baseline to Weeks 24, 48, 72, 104, 130, 156, 182 and 208 in peripheral blood biomarkers, including CXCL13, BAFF (B cell activating factor), TNF, IL-6, IL-10, IL-17, interferon-gamma, IL-4, IL-23, IL-8, soluble CD27 (sCD27), genetic risk factors (e.g., HLA-DRB1*15:01) or other emerging exploratory markers of disease biology as appropriate

Change from Baseline to Weeks 24, 48, 72, 104, 130, 156, 182 and 208 in patient reported outcomes, including quality of life, fatigue, depression, and disability, as measured by Neuro-QoL™

Change from Baseline to Weeks 24, 48, 72, 104, 130, 156, 182 and 208 in cognitive function and information processing speed as measured by symbol digit modality test (SDMT)

Correlation between changes in compartment-specific biomarkers of disease biology with radiologic and/or clinical disease outcomes

Correlation between changes in patient reported outcomes, including SDMT, and radiologic and/or clinical disease outcomes

Correlation between changes in compartment-specific immune cell subsets with radiologic and/or clinical disease outcomes.

Correlation between changes in NfL levels and radiologic and/or clinical disease outcomes

Correlation between changes in CSF abnormalities (OCB and IgG index) and radiologic and/or clinical disease outcomes

SAFETY OBJECTIVES

The safety objectives for this study are to evaluate the safety of ocrelizumab compared with placebo on the basis of the following endpoints:

Nature, frequency, severity, and timing of adverse events

Vital signs, physical findings, and clinical laboratory results during and following study drug administration

Adverse events related to biomarker sample collection

STUDY DESIGN

DESCRIPTION OF THE STUDY

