Treatment may be stopped at any time due to lack of clinical benefit, unacceptable toxicity, withdrawal of consent, patient or physician decision to discontinue treatment, death, or if the sponsor decides to close the trial, whichever occurs first.

Treatment of Radiologic Event

In the event of radiologic progression, in which a new contrast-enhancing or T2-weighted lesion suggestive of MS develops, the choice to continue or discontinue from the study

in order to initiate treatment with a DMT, including commercial OCREVUS®, is at the discretion of the treating physician. If a commercial disease modifying therapy is initiated, the participant will be discontinued from all study-related treatments.

Regardless of whether the participant is started on commercial disease modifying therapy, individuals with a radiologic event should complete study assessments until they have completed week 208 or until they have had a confirmed clinical relapse, whichever occurs first.

As described above in Section 4.4.1 treatment may be stopped at any time due to lack of clinical benefit, unacceptable toxicity, withdrawal of consent, patient or physician decision to discontinue treatment, death, or if the sponsor decides to close the trial, whichever occurs first.

Prohibited Therapy

The following therapies for MS are not permitted during the treatment portion of the study (through week 72): Other B-cell targeted therapies (e.g., rituximab, atacicept, belimumab, or ofatumumab, etc.), natalizumab, fingolimod, siponimod, alemtuzumab, daclizumab, cladribine, teriflunomide, dimethyl fumarate, diroximel fumarate, ozanimod, interferons, glatiramer acetate, cyclophosphamide, mitoxantrone, azathioprine, mycophenolate mofetil, cyclosporine, methotrexate, total body irradiation, bone marrow transplantation, IV Ig, plasmapheresis, other approved or investigational therapies for MS.

After patients have completed (or discontinued) treatment with study drug, they may receive alternative treatment for MS as judged clinically appropriate by the investigator. However, as sufficient data are not available regarding risks associated with switching to other products, the following recommendations are given:

Caution is advised if patients remain B-cell depleted.

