The above examples of dose interruption and slowing (for mild/moderate and severe IRRs) will result in a change in the infusion rate and increase the total duration of the infusion but not the total dose.

SAFETY PARAMETERS AND DEFINITIONS

Safety assessments will consist of monitoring and reporting adverse events (AEs) and serious adverse events (SAEs) per protocol. This includes all events of death and any study-specific issue of concern.

Adverse Events

An AE is any unfavorable and unintended sign (including an abnormal laboratory finding), symptom, or disease temporally associated with the use of an investigational medicinal product (IMP) or other protocol-imposed intervention, regardless of attribution.

This includes the following:

AEs not previously observed in the subject that emerge during the protocol-specified AE reporting period, including signs or symptoms associated with multiple sclerosis that were not present prior to the AE reporting period.

Complications that occur as a result of protocol-mandated interventions (e.g., invasive procedures such as cardiac catheterizations).

If applicable, AEs that occur prior to assignment of study treatment associated with medication washout, no treatment run-in, or other protocol-mandated intervention.

Preexisting medical conditions (other than the condition being studied) judged by the investigator to have worsened in severity or frequency or changed in character during the protocol-specified AE reporting period.

Serious Adverse Events

An AE should be classified as an SAE if the following criteria are met:

It results in death (i.e., the AE actually causes or leads to death).

It is life threatening (i.e., the AE, in the view of the investigator, places the subject at immediate risk of death. It does not include an AE that, had it occurred in a more severe form, might have caused death.).

It requires or prolongs inpatient hospitalization.

It results in persistent or significant disability/incapacity (i.e., the AE results in substantial disruption of the subject's ability to conduct normal life functions).

It results in a congenital anomaly/birth defect in a neonate/infant born to a mother exposed to the IMP.

It is considered a significant medical event by the investigator based on medical judgment (e.g., may jeopardize the subject or may require medical/surgical intervention to prevent one of the outcomes listed above).

Adverse Events of Special Interest

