AESIs are a subset of Events to Monitor (EtMs) of scientific and medical concern specific to the product, for which ongoing monitoring and rapid communication by the Investigator to the Sponsor is required. Such an event might require further investigation in order to characterize and understand it. Depending on the nature of the event, rapid communication by the trial Sponsor to other parties (e.g., Regulatory Authorities) may also be warranted.

Adverse events of special interest for this study include the following:

Cases of potential drug-induced liver injury that include an elevated ALT or AST in combination with either an elevated bilirubin or clinical jaundice, as defined by Hy's law:

Treatment-emergent ALT or AST $> 3 \times$ ULN in combination with total bilirubin $> 2 \times$ ULN

Treatment-emergent ALT or AST $> 3 \times$ ULN in combination with clinical jaundice

Data related to a suspected transmission of an infectious agent by the study drug (STIAMP), as defined below:

Any organism, virus, or infectious particle (e.g., prion protein transmitting transmissible spongiform encephalopathy), pathogenic or non-pathogenic, is considered an infectious agent. A transmission of an infectious agent may be suspected from clinical symptoms or laboratory findings that indicate an infection in a patient exposed to a medicinal product. This term applies only when a contamination of the study drug is suspected

There are no Ocrelizumab Events of Special Interest.

METHODS AND TIMING FOR ASSESSING AND RECORDING SAFETY VARIABLES

The investigator is responsible for ensuring that all AEs and SAEs that are observed or reported during the study, are collected and reported to the FDA, appropriate IRB(s), and Genentech, Inc. in accordance with CFR 312.32 (IND Safety Reports).

Adverse Event Reporting Period

The study period during which AEs and SAEs as described in Section 5.2 where the patient has been exposed to Genentech product must be reported. Reporting period begins after informed consent is obtained and initiation of study treatment and ends 24 weeks following the last administration of study treatment or study discontinuation/termination, whichever is earlier. After this period, investigators should only report SAEs that are attributed to prior study treatment.

Assessment of Adverse Events

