Population-level-summary estimator: The hazard ratio from a stratified Cox-proportional hazards model will be used. The stratified log-rank p-value will be used to test for statistical significance. Both will be stratified by the factors specified (see Section 4.2.1) for randomization.

Handling of missing data:

Withdrawal from study: a patient will be censored at the time of withdrawal from study.

Missing assessments at scheduled visits prior to last assessment: Missing data at scheduled visits prior to last assessment will not be imputed.

Secondary Efficacy Endpoints

The secondary endpoints for this study are to evaluate the efficacy and impact of ocrelizumab compared with placebo on the basis of the endpoints as described in Section 2.2.1 and biomarkers of disease activity and neuroaxonal damage in peripheral blood.

Each change from baseline for continuous secondary endpoints will be tested and analyzed using a stratified mixed-effects model for repeated measures (MMRM)

assuming missing at random (MAR). Sensitivity analyses will be conducted to assess the validity of this assumption,

For MRI related count endpoints (cumulative number of T2 lesions and T1 gadolinium-enhancing lesions), generalized linear methods appropriate for count data will be used depending on the distribution of the counts, e.g., a stratified negative binomial regression model.

Estimands for the Secondary Analyses

The estimands for the remaining secondary endpoints will have the same population and handling of missing data attributes as for the primary analysis.

Exploratory Efficacy Endpoints

Analyses on exploratory efficacy endpoints will be performed as data allows.

Exploratory efficacy endpoints are listed in Section 2.2.2. Further details will be described in the SAP.

SAFETY ANALYSES

The safety analysis population will consist of all randomized patients who received at least one dose of study drug, with patients grouped according to treatment received.

Safety will be assessed through summaries of exposure to study treatment, adverse events, changes in laboratory test results, and changes in vital signs and ECGs. Study treatment exposure (such as treatment duration, total dose received, and number of cycles and dose modifications) will be summarized with descriptive statistics.

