All verbatim adverse event terms will be mapped to MedDRA thesaurus terms, and adverse event severity will be graded according to CTCAE v5.0 grade. All adverse events, serious adverse events, adverse events leading to death, adverse events of special interest, and adverse events leading to study treatment discontinuation that occur on or after the first dose of study treatment (i.e., treatment-emergent adverse events) will be summarized by mapped term, appropriate thesaurus level, and severity grade. For events of varying severity, the highest grade will be used in the summaries. Deaths and cause of death will be summarized.

Associated laboratory parameters, such as hepatic function, renal function, and hematology values, will be grouped and presented together. Marked abnormalities will also be flagged.

BIOMARKER ANALYSES

Biomarkers will be assessed at baseline (screening) and subsequent time points following administration of ocrelizumab or placebo. Biomarkers levels at baseline or over time may be compared with efficacy or safety measurements to assess prognostic or

predictive properties. Biomarkers may also be analyzed over time as absolute values and/or percent change relative to baseline over time, and may be compared with efficacy, other biomarkers, or safety measurements.

INTERIM ANALYSES

The iDMC will review interim analyses as specified in the iDMC Charter. Interim analyses will be conducted by the unblinded statistician(s) and will focus on recruitment/enrollment, study conduct and safety.

No formal interim analyses for futility or efficacy are planned. However, the aggregate rate of the primary outcome will be monitored throughout the study to assure a sufficient number of events. The following scenario may trigger an interim look for futility.

If we are not on target to reach the hypothesized number of events (in the blinded dataset) by the end of the follow-up period, we will assess whether an extension to follow-up is fiscally feasible. If follow-up is feasible, a non-binding futility analysis using an alpha-spending function will be conducted to determine whether it is worth extending follow-up.

Similarly, we will monitor the current trend of treatment in this patient population. The following scenario may trigger an interim look for efficacy if applicable.

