collected on the same day as the ocrelizumab infusion, the blood samples should be collected prior to ocrelizumab administration. Blood sample collection may precede ocrelizumab administration by up to 4 weeks. Leftover biological samples will be stored by the central laboratory for later biomarker use. Please refer to the laboratory manual for additional details on laboratory assessments and sample handling.

ⁿ To be obtained/Performed before administration of ocrelizumab (i.e., pre-dose). Premedication with methylprednisolone and antihistamines should be given in accordance to the guidance provided in the USPI.

^o The first dose of study drug will be administered as two 300 mg IV infusions given 14 days apart. For the subsequent doses, study drug will be administered as a single 600 mg IV infusion at Weeks 24 and 48. A minimum interval of 22 weeks must be maintained between each 600 mg dose of study drug.

^p LP is required at baseline for subjects who have not previously had CSF analysis or who do not have access to source documentation (including oligoclonal banding testing) for prior CSF analysis. LP is optional at baseline for subjects who have previously had CSF analysis and have appropriate source documentation. LP is always optional at Weeks 104, 208, and unscheduled visits (in case of a clinical neurologic event), at the investigator's discretion. Local lab testing for CSF includes protein, cell count/differential, and oligoclonal banding. CSF oligoclonal banding results must be available prior to randomization and study drug administration. Baseline CSF may be collected up to 4 weeks prior to administration of study drug. If MRI and CSF are performed on the same day, MRI should precede the collection of the CSF specimen and study drug infusion, and the CSF specimen collection should precede the study drug infusion. Blood biomarker samples should be collected as close as possible in time to the CSF sample, which may be prior to study drug administration by up to 4 weeks.

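### Section 6.5 sets no end to the adverse-event window and no rule for time on another MS therapy, and it describes no table for events from the pre-dose lumbar puncture

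*Combined protocol and SAP*

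**What the plan says.** **Safety tables (Section 6.5).** Adverse events "that occur on or after the first dose of study treatment (i.e., treatment-emergent adverse events) will be summarized by mapped term", "with patients grouped according to treatment received". No end date is given, and nothing is said about time after another MS therapy starts.

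**After a radiologic event (Section 4.4.2).** The treating physician may start a DMT, commercial ocrelizumab included. Study treatment then stops, but "individuals with a radiologic event should complete study assessments until they have completed week 208 or until they have had a confirmed clinical relapse", whether or not a DMT was started.

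**After a confirmed clinical relapse (Sections 3.1 and 4.4.1).** The patient is discontinued from the study.

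**How long events are collected.** Two rules conflict.
- Section 5.3.1 opens collection only once the patient has consented and been dosed. As for its close, the period "ends 24 weeks following the last administration of study treatment or study discontinuation/termination, whichever is earlier". Afterwards only serious events attributed to prior study treatment are reported.
- Appendix 1, footnote u, has adverse events reported throughout the study, and the schedule marks them from screening to Week 208.

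**Lumbar puncture.** Section 2.3 lists "Adverse events related to biomarker sample collection" among the safety endpoints. Section 5.2.1 counts as adverse events those before treatment assignment that are "associated with medication washout, no treatment run-in, or other protocol-mandated intervention". Appendix 1, footnote p, says "Baseline CSF may be collected up to 4 weeks prior to administration of study drug", and the text on CSF samples keeps the remainder as a biomarker sample. Section 4.2.1 and footnote p require this puncture only for participants without documented earlier CSF analysis.

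**The concern.** The safety objective is to compare ocrelizumab with placebo. A placebo patient who develops a new lesion, starts commercial ocrelizumab and then has an infusion reaction or infection would appear in the placebo column. The plan expects more events on placebo than on ocrelizumab (33% against 20% by 4 years), so this crossover is unequal between arms and tends to hide drug-related events. The primary estimand in Section 6.4.1 names initiation of another MS therapy as an intercurrent event and gives it a strategy. The safety section gives none, although there the added drug can be the test drug itself.

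The second gap is separate. The baseline lumbar puncture comes before dosing, so its complications, if they begin before the first dose, fall outside the only window described. A participant who has the puncture but is never dosed is also outside the safety population.

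**Working it through.** The plan states no figure for time on other therapy, so there is none to reproduce. The steps below compare the two collection rules and then gauge the scale.

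**1. Collection windows.** The last planned dose is at Week 48. Under Section 5.3.1, routine collection for a fully dosed patient ends at Week 48 + 24 = Week 72. The remaining 208 - 72 = 136 weeks (136/208 = 65%) are covered only under footnote u.

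**2. Hazards from the plan's rates (Section 6.1), taken as exponential.**
- Placebo: -ln(0.67)/4 = 0.1001 per year.
- Ocrelizumab: -ln(0.80)/4 = 0.0558 per year.
- Dropout of 10% a year: -ln(0.90) = 0.105 per year.

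**3. Ceiling: every event radiologic, every patient starting a DMT at the detecting scan, no dropout.** Scans are at Weeks 24, 48, 72, 104, 156 and 208. The chance of first detection at scan k is exp(-λm₍k-1₎/52) - exp(-λm₍k₎/52).
- Placebo: 0.0452, 0.0431, 0.0412, 0.0520, 0.0780, 0.0706.
- Ocrelizumab: 0.0254, 0.0248, 0.0241, 0.0312, 0.0485, 0.0459.

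*Footnote u.* Share = Σ p₍k₎(208 - m₍k₎)/208.
- Placebo: (0.0452×184 + 0.0431×160 + 0.0412×136 + 0.0520×104 + 0.0780×52)/208 = 14.6%.
- Ocrelizumab, same formula: 8.5%.

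*Section 5.3.1, counted from each patient's own last dose, with the dose due at the detecting visit given.* Detection at Week 24 or 48 leaves 24 weeks on DMT inside the window.
- Placebo: 24×(0.0452 + 0.0431)/(72 - 24×0.0452) = 2.12/70.92 = 3.0%.
- Ocrelizumab: 24×(0.0254 + 0.0248)/(72 - 24×0.0254) = 1.7%.
- If the dose due at that visit is not given, the shares fall to 0.13% and 0.07%.

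**4. Placebo arm with dropout and partial uptake.** This is a simulation of 50 patients with the hazards above. Clinical events end follow-up. These assumptions are not in the documents: 50-100% of events are radiologic, 25-100% of those patients start a DMT at detection, the dose due at the detecting visit is given, and dropout continues at the same rate after an event.

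| Radiologic share | DMT uptake | Footnote u: patients of 50 | Footnote u: share of time | Section 5.3.1: patients of 50 | Section 5.3.1: share of time |
|---|---|---|---|---|---|
| 100% | 100% | 10.9 | 13.6% (22.1 of 163.2 person-years) | 4.1 | 2.9% (1.86 of 63.5) |
| 100% | 50% | 5.5 | 6.8% (11.1 of 163.2) | 2.1 | 1.4% (0.93 of 64.0) |
| 75% | 50% | 4.1 | 5.3% (8.3 of 156.5) | 1.5 | 1.1% (0.69 of 63.0) |
| 50% | 25% | 1.4 | 1.9% (2.8 of 149.8) | 0.5 | 0.4% (0.24 of 62.2) |

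**5. What a share s does to the comparison.** Suppose events occur at rate r₀ on placebo and r₁ on ocrelizumab, and the added drug also carries r₁. The placebo column then shows (1 - s)r₀ + s·r₁, and the observed difference is (1 - s)(r₁ - r₀). Under that simplification the rate difference shrinks by the share itself. Section 6.5 does not mention exposure adjustment. In a plain count of patients with an event, the number of patients exposed matters as well.

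**6. Lumbar puncture.** This part is a comparison of text. The event is an adverse event under Section 5.2.1 and bears on an endpoint in Section 2.3. Under the schedule it is collected from screening; under the start rule in Section 5.3.1 it may not be. If it begins before the first dose, it is outside the Section 6.5 window, and no other table is described. If Section 5.3.1 governs, routine events from the optional punctures at Weeks 104 and 208 are missed too, because both fall after Week 72.

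**The case against.** **A table can hold only what is collected.** If Section 5.3.1 governs, little crossover time enters the tables. This stands, and it is why the size must be given under both rules. It does not remove the point: footnote u says the opposite, and the share is above zero under either rule.

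**A reader might infer that 15% to a third of placebo follow-up is affected.** The 14.6% is a ceiling that needs footnote u to prevail, no dropout, full uptake and no clinical events. A figure near a third (31.8% placebo, 19.9% ocrelizumab) comes only from also treating the background remark on a 2.7-year median to radiologic progression as an exponential median for all patients, which that ambiguous sentence does not establish. Confirmed relapses leave the study, and the plan itself assumes 10% annual dropout.

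**A reader might infer that the window is wrong at its start, or that 100 mandatory punctures go untabulated.** Neither is supported. Starting at first dose is a proper definition for an arm comparison, and a puncture done before randomization cannot inform that contrast. The puncture is required only without documented prior CSF analysis, so 100 is a ceiling. The documents give no complication rate, so no event count can be stated. Blood-draw events after dosing remain in the window.

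**Following the whole arm is a coherent safety summary, and stopping at DMT start has its own bias.** This also stands. Such censoring depends on disease activity and could drop delayed effects; the risk section gives a median B-cell repletion time of 72 weeks. Both tables are therefore needed.

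**A fuller SAP may settle this.** Section 6 defers details to one, and no separate SAP text was available. Concomitant therapies are recorded, so a split could be made later, but a rule set after unblinding would be post hoc.

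**Conclusion.** Two gaps hold on the text. Section 6.5 sets no end to the window and no rule for another MS therapy, so events on commercial DMT can be counted under placebo and bias the comparison toward no difference. Under the assumptions in step 4, about 2-14% of placebo adverse-event time (1.4 to 10.9 of 50 patients) is affected under footnote u, and about 0.4-3% (0.5 to 4.1 patients) under Section 5.3.1. The direction assumes that the added drug raises event rates. The simulation counts only DMT started at a radiologic event. Section 4.4 also allows other MS treatment after study drug is completed or discontinued, and that is not included.

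Pre-dose lumbar puncture events relate to a stated endpoint but have no described table. That calls for a descriptive listing and leaves the treatment-emergent definition as it is. The whole point is a cheap improvement; it does not show that the safety analysis is invalid.

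**What to change.** - Reconcile Section 5.3.1 with Appendix 1, footnote u and the schedule, at both the start and the end of collection.
- In Section 6.5, add an exposure-adjusted adverse-event comparison by arm that stops at the first dose of any non-study MS therapy. Tabulate later events separately by the drug then being taken.
- Keep the whole-study table beside it, and say why: stopping at DMT start depends on disease activity and may miss delayed effects.
- Add a descriptive listing of adverse events attributed to sample collection, from the first study procedure and whether or not the participant is dosed. Leave the treatment-emergent start at first dose unchanged.

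The cost is SAP wording and two extra tables, with no change to patient procedures. The downside is that the added comparison has a shorter window and is informatively censored. The rule should be fixed before unblinding.
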